## 5.7. Multiple Comparisons/Multiplicity

At the time of the unblinded interim analysis, only the first secondary efficacy endpoint ALA levels at Month 3 will be assessed. A significance level of 0.001 will be used when comparing the ALA levels between the two treatment arms using an ANCOVA model.

For the final analyses of the 6m-DB primary treatment period, a significance level of 0.049 will be used to test the efficacy endpoints, reflecting a penalty of 0.001 for the unblinded interim analysis. A fixed-sequence testing strategy for the primary and secondary endpoints will be implemented to control the overall type I error rate. The primary endpoint will be compared between treatment arms at the significance level of 0.049. If the test is statistically significant, then the secondary endpoints will each be tested at the same significance level of 0.049 in the order specified in the efficacy endpoint section (Section 3.2 ). If the test of an endpoint in the sequence is not statistically significant, the testing of remaining endpoints in the sequence will stop and the null hypotheses for the subsequent tests will not be rejected.

There will be no multiplicity adjustment for exploratory endpoints.

## 5.8. Analysis Cutoff and Database Lock

For the interim analysis and the final 6m-DB analysis, as this study will be ongoing, the study database will be soft-locked with all data up to a prespecified cutoff date quality controlled, i.e. data in EDC will be frozen and external data such as laboratory data will be QA'd and cleaned.

The soft lock is an interim database lock. Additional details regarding the soft lock process are located in the study Data Management Plan.

The interim and the final 6m-DB analysis will include data on or prior to this prespecified cutoff date. For assessments with starting/ending dates (e.g., AEs, medications, medical history), the starting date will be compared with the pre-specified cutoff date.

After the study is completed, i.e., all patients completed the OLE period and the safety follow-up visits, the database will be hard locked and all data collected will be used for analysis.

## 5.9. Interim Analyses

An unblinded interim analysis will be conducted when approximately 40 AIP patients have completed the Month 3 visit. The data for these ~40 patients will be soft-locked for an interim database lock and transferred in support of the interim analysis. A cutoff analysis approach will be implemented in the analysis datasets as specified in Section 5.8 . The details of the interim analyses are discussed in Appendix 9.1

## 5.10. Analyses for the Entire Study

The study design includes a 6m-DB period and an OLE period. The primary objective is to evaluate the efficacy and safety of givosiran compared with placebo during the 6m-DB period. In addition, the long-term efficacy and safety of givosiran during the entire givosiran treatment period (beyond 6m-DB) will be characterized for the All Givosiran Treated Set. For patients who received placebo in the 6m-DB period and givosiran in the OLE period, the intra-patient comparison of the two treatment periods will be conducted to assess the trajectory changes for selected efficacy parameters.

The detailed definitions for different treatment periods are as the following.

- **6m-DB Period**

The treatment comparison of givosiran versus placebo will focus on the 6m-DB period, defined as below:

- 1) For patients who received at least one dose of givosiran during the OLE period, all assessments collected prior to the first dose of givosiran in the OLE period will be included in the 6m-DB period. All data will be included in the summary tables and figures.
- 2) For patients who discontinued treatment and did not receive any givosiran dose in the OLE period, all assessments will be included in the 6m-DB period. Assessments collected within given time windows (details listed in below table) will be included in summary tables/figures and those outside the time windows will be listed only unless specified otherwise (e.g., AEs in Section 6.8 ).

Endpoint	Windowing rule for patients who did not enter OLE
Safety and PD endpoints	Assessments with onset date within 28 days of the last dose [1]
Attacks and hemin use related endpoints	Data collected on or before the earlier of 1) Day 162 which is the start day of Month 6 visit window; and 2) end of study (EOS) date.

Endpoint	Windowing rule for patients who did not enter OLE
Other clinical efficacy endpoints	Assessments collected on or before Day 183.

[1] In a rare situation that a patient did not discontinue 6m-DB and did not enter OLE, all data will be included in summary. For AE summary, related AEs will be considered as TEAE and included in summary tables regardless of time window.

- **OLE Period**

The start day of the OLE period is defined as the day when the first dose of the OLE period is administered. The assessments collected or AEs with onset after the administration of the first dose of the OLE period will be included in the OLE period. When assessments or AE onset dates are exactly the first OLE dose date with time missing, the records will be included in the OLE period.

- **During Givosiran Treatment**

For all patients who received at least one dose of givosiran, data will be summarized for the “during givosiran treatment” period, defined as below.

- 1) For patients who received givosiran in the 6m-DB period, all assessments collected after the first dose of givosiran during the entire study including both the 6m-DB and OLE periods (if available) will be included in the “during givosiran treatment”.
- 2) For patients who received placebo in the 6m-DB period and switched to givosiran in the OLE period, all assessments collected after the first dose of givosiran in the OLE period will be included in the “during givosiran treatment”.
- 3) For patients who discontinued givosiran treatment during the 6m-DB period, the data handling will follow the same rules as discussed above for “6m-DB period”. For discontinuation in the OLE period, assessments within 28 days of the last dose of givosiran will be included in summaries. For ongoing patients, all data are included.

Selected efficacy parameters will be summarized over the entire study including the 6m-DB and OLE periods for all patients to show the trajectory changes comparing the placebo experience versus the givosiran experience, for example, summary of creatinine normalized urinary ALA by visit. In these summaries, the treatment groups are “Givosiran” or “Placebo” based on randomization during the 6m-DB period.

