## 5.6. Visit Windows

For PD and clinical laboratory parameters, analysis visits will be derived for the 6m-DB period based on the study day and visit windows. Target days and the acceptable range of study days for each visit are defined in [Table 1](#) below. If more than one visit falls within a visit window, the visit occurring closest to the target day will be selected. If there are multiple visits with the same distance from the scheduled visit day, the later visit will be selected. The derived visits will be used for all analyses.

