**Table 1: Derived Analysis Visit Windows**

Study Visit	Target Day	Window
Screening	Day -60 to -1	$\leq -1$
Day 1	1	1
Week 2	15	2 – 22
Month 1	29	23 – 43
Month 2	57	44 – 71

Study Visit	Target Day	Window
Month 3	85	72 – 106
Month 4	113	107 – 127
Month 5	141	128 – 155
Month 6	169	156 - the earlier of (Day 183, and the day of the first dose of OLE)

For PD and laboratory parameters assessed during the OLE period and for vital signs and ECG measurements during the entire study, no windowing rules will be implemented, and the reported clinical visits will be used for analysis.

For QOL assessments including SF-12, EQ-5D-5L and missed days of work/school, data are collected every 3 months up to 12 months, then every 6 months afterwards. If the scheduled visits are not performed, any unscheduled and/or discontinuation visits will be mapped to the corresponding scheduled visits if the visit dates fall into below windows. The midpoint of two visits will be included in the time window of the preceding visit.

Scheduled visits (Month 3, 6, 9, 12)  $\pm$  6 weeks

Scheduled visits (Month 18, 24, 30, 36)  $\pm$  12 weeks

For patients who switched from placebo to givosiran, study visits will be mapped based on the redefined baseline.

The derived visits will be used for analyses.

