## 6.6. Pharmacodynamic Analysis

Analyses of secondary endpoints relating to ALA and PBG levels are described in Section 6.5.2. In addition, ALA, PBG, and ALAS1 levels will be summarized descriptively at each scheduled visit.

Population PK/PD analyses will be described in a separate population PK/PD analysis plan.

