## 9. APPENDICES

### 9.1. Details of Interim Analysis

At the interim, the only efficacy endpoint to be assessed is the Month 3 ALA level in AIP patients. The other efficacy endpoints will not be analyzed. ALA data beyond 3 months will be summarized descriptively by treatment arm for each scheduled visit during the 6m-DB period. Patient disposition, demographic and baseline characteristics, drug exposure, safety, PK, and PD will be summarized as described in Section 6 .

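### The SAP has two competing data rules for ALA and PBG after treatment discontinuation (28 days from last dose in 5.10, study day alone in 5.6), and 6.5.2 does not say which one governs the MMRM

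*SAP*

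**What the plan says.** SAP 5.10 defines the double-blind period for the givosiran-versus-placebo comparison. For a patient who discontinued and took no open-label dose, it first says that "all assessments will be included in the 6m-DB period". It then restricts what enters summary tables and figures by endpoint type. One row groups safety with PD and allows "Assessments with onset date within 28 days of the last dose"; "those outside the time windows will be listed only unless specified otherwise". The attack and hemin row stops at the earlier of Day 162 and end of study, and the row for other clinical efficacy endpoints stops at Day 183. Neither refers to the last dose. Footnote [1] keeps all data for a patient who neither discontinued the double-blind period nor entered the extension.

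SAP 5.6 derives PD visits in the double-blind period from study day and adds: "The derived visits will be used for all analyses". In its Table 1, Month 3 is Day 72 to 106, and Month 6 is "156 - the earlier of (Day 183, and the day of the first dose of OLE").

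SAP 6.5.2 runs the ALA and PBG MMRM in FAS_AIP. The only exclusion it names is for values within 3 days after hemin, and it cites neither 5.6 nor 5.10. SAP 6.6, the pharmacodynamic section, says: "Analyses of secondary endpoints relating to ALA and PBG levels are described in Section 6.5.2". SAP 5.7 and 9.1, by contrast, class Month 3 ALA as an efficacy endpoint: "the only efficacy endpoint to be assessed is the Month 3 ALA level in AIP patients".

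Protocol Table 1 (footnote b) and Section 5.3.1 ask patients who stop treatment to continue assessments through Month 6.

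**The concern.** A Day 169 ALA value from a patient last dosed on Day 85 is a Month 6 record under 5.6 and listing-only under 5.10. Applying the two rules in sequence does not reconcile them; it only means that 5.10 wins. Three alpha-controlled secondary endpoints are affected: ALA at Month 3, ALA at Month 6 and PBG at Month 6.

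A 28-day cut also fits poorly with the rest of the plan. FAS_AIP is analysed as randomized, the protocol collects the samples through Month 6, and SAP 6.5.1.1 counts attacks after discontinuation. SAP 9.3 assumes that the drug effect lasts up to 56 days. If off-drug values are dropped, the MMRM treats them as missing at random and in effect predicts them from the patient's earlier on-drug values and the arm mean. Relative to an as-randomized target, this favours givosiran whenever ALA or PBG rises after stopping.

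**Working it through.** **The plan's own ALA figure.** SAP 9.1.2 gives Month 3 means (SD) of 20.0 (11.1) on placebo and 2.3 (1.1) on givosiran, and more than 90% power with 40 AIP patients at 0.001. With 20 per arm, SE = sqrt((11.1² + 1.1²)/20) = 2.494 and 17.7/2.494 = 7.10. Power = Φ(7.10 − 3.29) = 99.99%, or 99.7% with a Welch t. The stated figure is confirmed.

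**Which values the 28-day rule drops.** Scheduled double-blind doses fall on Days 1, 29, 57, 85, 113 and 141 (Protocol Table 1). The last day kept is the last dose day + 28.

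| Last dose | Kept to | Days off drug at Day 169 | Month 3 days kept (72–106, 35 days) | Month 6 days kept (156–183, 28 days) |
|---|---|---|---|---|
| Day 1 | 29 | 168 | 0 | 0 |
| Day 29 | 57 | 140 | 0 | 0 |
| Day 57 | 85 | 112 | 14 (72–85) | 0 |
| Day 85 | 113 | 84 | 35 | 0 |
| Day 113 | 141 | 56 | 35 | 0 |
| Day 141 | 169 | 28 | 35 | 14 (156–169) |

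A Month 4 dose given 7 days late (Day 120) reaches only Day 148, so Month 6 is still lost. After a Day 141 dose, 8 of the 15 protocol visit days (Day 162 to 176) are kept and 7 are lost. This last row applies only if the patient is recorded as having discontinued; otherwise footnote [1] keeps everything. Under 5.6, every value in the two windows is kept.

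**Size for Month 6 ALA.** Assumptions: the Month 3 planning means hold at Month 6, there are 35 AIP patients per arm (70 randomized 1:1), k givosiran patients more than 56 days off drug have their values dropped, and each returns a fraction r of the way to the placebo level. On the dosing schedule these are patients last dosed at Month 3 or earlier (84 days or more at Day 169).

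- SE with values dropped = sqrt((11.1² + 1.1²)/35) = 1.885; z = 17.7/1.885 = 9.4.
- Overstatement = k × r × 17.7/35.
- k = 1: 0 at r = 0; 0.25 (1.4%, 0.13 SE) at r = 0.5; 0.51 (2.9%, 0.27 SE) at r = 1.
- k = 2: 0; 0.51 (2.9%, 0.27 SE); 1.01 (5.7%, 0.54 SE).

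A simulation with an unstructured-covariance likelihood model (arm-by-visit means, no other covariates, assumed within-patient correlation 0.7) gave the same mean shifts to within 0.01.

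**Effect on the test with values kept, r = 1.** For k = 2 the difference is 17.7 − 1.01 = 16.69. If returned patients have the givosiran SD (1.1), the givosiran-arm variance is 1.21 + (2/35)(33/35)(17.7²) = 18.09. Then SE = sqrt((123.21 + 18.09)/35) = 2.01 and z = 8.3. If they have the placebo SD (11.1), the variance is 25.06, SE = 2.06 and z = 8.1. For k = 1, z is 8.8 or 8.7.

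**The pattern-mixture safeguard.** SAP 6.5.2 triggers it at 5% or more on the givosiran arm; 9.3 says above 5% and names no arm. One of 35 is 2.9% and does not trigger it. Two of 35 is 5.7% and does under 6.5.2, but two of 70 is 2.9% and would not if 9.3 means both arms together. Drop-out is not defined, and the analysis covers ALA, not PBG.

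**The case against.** The best defence is that 5.10 was never meant to reach the MMRM. The 28-day row speaks of onset dates, which suits events better than urine samples, and the restriction is worded for summary tables and figures. SAP section 4 assigns the PD set to PD analyses, while 6.5.2 uses FAS_AIP. The hemin exclusion in 6.5.2 might count as a case specified otherwise. The Day 183 limit in Table 1 would also never bind for these patients under a 28-day rule: a Day 141 dose reaches Day 169, and one given 7 days late reaches Day 176.

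These points show that 5.10 is not the only reading, but they do not settle the matter. The same table introduces the between-arm comparison, and its attack row sets the window for the primary endpoint, so it is not confined to descriptive output. SAP 6.6 also places ALA and PBG under pharmacodynamics.

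An on-treatment biomarker analysis is a legitimate choice, and the SAP states no estimand for these endpoints. The overstatement is therefore relative to an as-randomized target. The pattern-mixture analysis is a partial safeguard for ALA: it imputes from placebo when there was no dose within 56 days, which is close to r = 1. Protocol 5.3.1 allows local standard treatment after stopping, which could reduce or alter any rise.

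A reader might infer that most discontinued patients lose their Month 6 value. The documents do not support that. Five of the six possible last-dose visits lead to loss, but stopping times are not given, and footnote [1] protects patients not recorded as discontinued.

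**Conclusion.** The gap is real and worth closing. It goes beyond a missing cross-reference, because following a stated rule would discard collected values from alpha-controlled endpoints. On the planning means, the Month 6 ALA difference would be overstated by at most about 0.5 mmol/mol (2.9%, 0.27 SE) per affected givosiran AIP patient. The overstatement is zero if ALA stays at the on-drug level. The number of affected patients is not in the documents and may be zero. No PBG planning values are given; under the same assumptions, the proportional shift would be r/35 per patient.

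Two stronger readings should be resisted. The documents do not establish that the 28-day rule governs the MMRM; they leave it open. Nor do they suggest that the ALA conclusion is at risk: z stays at about 8 or more with up to two values kept. What is at stake is the estimates, their confidence intervals, and an avoidable analyst choice.

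**What to change.** In the SAP 5.10 table, give the ALA and PBG secondary endpoints their own row, separate from safety. In 6.5.2, state that the main MMRM uses all values in the 5.6 windows before any open-label dose, regardless of treatment discontinuation, keeping the existing 3-day hemin exclusion and adding no other. Report the 28-day on-treatment version as supportive. Align the pattern-mixture trigger between 6.5.2 and 9.3 (threshold, arm and definition of drop-out).

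The cost is one table row and a few sentences; the samples are already scheduled. The estimates may be slightly less favourable and more variable. SAP Amendment 2 was to be signed before unblinding, but the supplied protocol is later and its Section 1.4 already cites open-label results. If the data are already unblinded, the report should state which rule was applied and show both versions.

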- ^l For females of child-bearing potential, a serum pregnancy test will be performed at Screening; thereafter, serum or urine pregnancy tests will be performed monthly. Results must be available before dosing.
- ^m At the Month 6 visit, the first open-label dose of givosiran in the extension study will be administered after all scheduled 6-month assessments (for the completion of the double-blind period) have been performed. The urine ALA and PBG sample must be collected prior to the first open-label dose of givosiran. If the ALA and PBG sample collection is delayed due to hemin usage within 4 days of the Month 6 visit, the open-label dose should be delayed as well.
- ⁿ In patients who were on hemin prophylaxis prior to study, collection of the Screening urine samples for ALA, PBG, and ALAS1 mRNA must occur when the patient is not having an attack, and \geq 4 days after prophylactic hemin discontinuation and after their last hemin dose. Two screening urine samples (collected on 2 different days) should be collected for ALA/PBG; one screening urine sample should be collected for ALAS1 mRNA. During the study, spot urine samples for ALA, PBG, and ALAS1 mRNA measurement should be collected prior to study drug dosing; however, if hemin is used for an attack, scheduled urinary ALA, PBG and ALAS1 mRNA will be collected 4 days (+4 days) after the patient's last hemin dose. At the Month 6 visit, the first open-label dose of givosiran should not be administered until the Month 6 urine sample for ALA, PBG have been collected. Where applicable country and local regulations and infrastructure allow, Screening and on-study urine samples for ALA, PBG, and ALAS1 mRNA assessments may be collected by a home healthcare professional, sent to the study center by mail, or brought to the study center at the next visit.

- ^o Where allowed per local regulations and IRB/EC approval, serum, plasma, and urine samples for exploratory biomarker testing, and measuring homocysteine levels, will be collected prior to dosing.
- ^p Genetic testing of porphyria-related genes is only required in patients without prior documented genetic testing for porphyria. See Section 7.6.2 for details.
- ^q Where allowed per local regulations, IRB/IEC approval, and patient consent (and assent, where applicable), a voluntary blood sample may be collected for later DNA analysis. See Section 7.6.2 for details.
- ^r Sample to be collected predose.

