6.2.2.1. During the 6-Month Treatment Period (Day 1 to Month 6)

Patients will be administered givosiran 2.5 mg/kg or placebo as an SC injection once a month.

To maintain the blind, the syringes are to be masked prior to study drug withdrawal from the masked vial. At the Month 6 study visit, following the completion of all Month 6 assessments, including the urine sample for ALA and PBG levels (to end the double-blind period), patients will be administered their first open-label (unmasked) dose of givosiran to begin their participation in the open-label extension portion of the study.

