The SF-12 scores are obtained using the Optum (PRO CoRE 1.3 Smart Measurement® System) software with the 2009 U.S. general population t-scores applied. For the Physical Component Summary (PCS) of SF-12 score, change from baseline at Month 6 in AIP patients (FASAIP) will be analyzed using an MMRM model with baseline score as a continuous covariate, fixed effect terms including treatment arms, stratification factors, visit (Month 3 or Month 6), and visit by treatment interaction.

All secondary endpoints defined for the AIP patients will also be analyzed for the AHP patients using similar methods.

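### SAP 5.10 sends untimed assessments dated on the first open-label dose day to the OLE period, although the protocol schedules Month 6 assessments before that dose

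*SAP*

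**What the plan says.** **Order at Month 6.** Protocol Table 1, footnote m, states that the first open-label dose "will be administered after all scheduled 6-month assessments (for the completion of the double-blind period) have been performed". Section 6.2.2.1 repeats the order: the dose comes "following the completion of all Month 6 assessments, including the urine sample for ALA and PBG levels".

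**Period assignment.** For patients who enter the OLE, SAP 5.10 states that "all assessments collected prior to the first dose of givosiran in the OLE period will be included in the 6m-DB period". Under its OLE heading it adds: "When assessments or AE onset dates are exactly the first OLE dose date with time missing, the records will be included in the OLE" period. The rule names assessments as well as AE onsets and makes no exception for scheduled Month 6 visits.

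**Visit windows.** In SAP 5.6, Table 1, the Month 6 window runs from Day 156 to "the earlier of (Day 183, and the day of the first dose of OLE". That table covers PD and clinical laboratory parameters only. The separate rule for quality-of-life instruments maps unscheduled or discontinuation visits when a scheduled visit was not done. It does not address a scheduled Month 6 form dated on the dose day.

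**Baseline.** For most measures, SAP 5.4 counts values up to and including the first-dose day as pre-dose. It derives the redefined baseline of placebo patients who switch to givosiran in a similar way.

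**Endpoint.** SAP 6.5.2 analyzes SF-12 PCS "change from baseline at Month 6 in AIP patients" with an MMRM that has two post-baseline visits, Month 3 and Month 6.

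**The concern.** When a patient follows the schedule, the Month 6 assessment and the first open-label dose fall on the same date. The tie that SAP 5.10 resolves is therefore the planned case and not a rare one. Sending an untimed AE onset on that day to the OLE period is reasonable. Sending an untimed scheduled assessment there assumes that it followed the dose, which is the reverse of the protocol order.

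SF-12 PCS at Month 6 is a secondary endpoint in the fixed sequence tested at 0.049 (SAP 5.7). EQ-5D-5L and PGIC are exploratory, but Month 6 is the only double-blind PGIC measurement and SAP 6.5.3 plans a between-arm test of it. If same-day values were lost, the Month 6 values left would come from patients dosed on a different day and from patients who never entered the OLE. Footnote m delays the dose when recent hemin use delays the urine sample, and patients who do not enter the OLE keep values through Day 183 (SAP 5.10). The remaining patients would be a selected group.

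**Working it through.** The plan gives no figure on this point to reproduce. The check applies the rules to example records and then shows what a loss would mean.

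**1. Apply the two rules to an untimed, scheduled Month 6 record.** Inputs are the SAP 5.10 tie rule and the SAP 5.6 Table 1 window (Day 156 to the earlier of Day 183 and the first OLE dose day).

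| Record | First OLE dose | SAP 5.10 | SAP 5.6 Table 1 (PD and laboratory only) |
|---|---|---|---|
| Day 169 | Day 169 | OLE | Month 6, double-blind |
| Day 176 | Day 176 | OLE | Month 6, double-blind |
| Day 162 | Day 169 | double-blind | Month 6, double-blind |
| Day 169 | Day 170 | double-blind | Month 6, double-blind |

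Only same-day records are affected. For untimed PD and laboratory samples the two sections give opposite answers. A timed pre-dose sample satisfies both.

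**2. Compare with the baseline convention.** Take a placebo patient with an untimed Month 6 SF-12 on the dose day. Under SAP 5.4 that value can serve as the pre-givosiran baseline. Under SAP 5.10 the same value is an OLE assessment.

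**3. Which instruments are exposed.** Month 6 vital signs, ECG and PK have scheduled pre-dose and post-dose times (protocol Table 1 footnotes h and j; Tables 8 and 9). The protocol specifies no clock time for SF-12, EQ-5D-5L or PGIC (Table 1 footnotes; Section 7.2.4). Whether the data-capture system records one is not stated.

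**4. Size, by assumption.** Let q be the share of the planned 70 AIP patients whose Month 6 SF-12 is both same-day and untimed, and suppose that those values are dropped. Then 70 × (1 − q) values remain, and the standard error of a simple Month 6 comparison is multiplied by 1/√(1 − q).

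| q (assumed) | Values left | SE multiplier |
|---|---|---|
| 0 | 70 | 1.00 |
| 25% | 52.5 | 1.15 |
| 50% | 35 | 1.41 |
| 75% | 17.5 | 2.00 |
| 90% | 7 | 3.16 |
| 100% | 0 | no Month 6 contrast |

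The multiplier is for a simple comparison. The MMRM would recover some precision from Month 3, by an amount that depends on a correlation the documents do not give.

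**The case against.** The strongest reply is that SAP 5.10 assigns records to periods, whereas SF-12 PCS, EQ-5D-5L and PGIC are analyzed by visit. A programmer could keep a form under its nominal Month 6 visit whatever its period flag says, and no text says that the flag removes the visit label. That stands as a reason not to claim a certain loss. Equally, no text says that the nominal visit prevails, and a prespecified confirmatory analysis should not depend on that choice.

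Second, the rule applies only when the time is missing, and the documents do not show that these forms are untimed. This also stands, and it is why the range starts at 0.

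Third, the Table 1 window suggests that the authors meant Month 6 data on the dose day to be double-blind data. That supports the fix, but the table does not extend to the quality-of-life instruments.

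Fourth, the consequence is limited. SF-12 PCS is last in the testing sequence, so no later test depends on it, and for ALA and PBG the window that includes the dose day is the more specific rule. Both points are correct.

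Two stronger readings are tempting. A reader might infer that placebo patients' Month 6 values would be counted as data collected on givosiran. The documents do not support this: SAP 5.10 defines the givosiran-treatment period separately, as what was collected after the first givosiran dose, with no missing-time default, and SAP 5.4 treats such values as pre-givosiran baseline. A reader might also infer that everything done at Month 6 precedes the dose. It does not: some vital signs, ECG and PK measurements are scheduled after it.

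**Conclusion.** The point holds as a misdirected default in SAP 5.10. Followed literally, it assigns scheduled pre-dose assessments to the wrong period, and it is inconsistent with SAP 5.6 (for untimed PD and laboratory data) and with SAP 5.4.

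Loss of data from the double-blind comparison is conditional on two things that the documents leave open: that the forms carry no clock time, and that the period flag overrides the nominal visit. If both hold, same-day Month 6 values of SF-12 PCS, EQ-5D-5L and PGIC drop out. The share is unknown, between 0 and 100%, and the intermediate figures above are assumptions. The primary attack-rate endpoint is not shown to be affected, and no alpha, power or sample-size figure changes. The correction should be made because it is nearly free and protects a confirmatory endpoint.

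**What to change.** In SAP 5.10, limit the missing-time default to AE onsets and other event-type records. Then add a sentence such as: scheduled Month 6 assessments dated on the first OLE dose date with time missing are assigned to the 6m-DB period, except those identified as post-dose (vital signs, ECG and PK measurements at post-dose time points, and post-dose urine collections at East Asian centers). This follows the protocol order and agrees with SAP 5.6 Table 1.

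The protocol's Amendment 5 summary already reports double-blind results. If that analysis used this text, confirm and document how same-day Month 6 records were assigned.

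The cost is a short edit to one SAP section. The downside is that a form completed after the dose, against protocol and with no time recorded, would be kept as pre-dose. That should be rare.
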